5.0 Enrollment/Randomization

The research will be designed as a single center study, where patient recruitment will be conducted by the participating surgeon at UCSF. The initial evaluation will be conducted while the surgeon is evaluating the patients. The final eligibility of each patient for participating in this study will be determined by the participating surgeon in accordance of his/her medical conditions. Following the exclusion criteria, the study will aim to accrue all eligible patients who are going to the OR as part of their standard surgical procedure.

All participants must be provided a consent form describing the study with sufficient information for each participant to make an informed decision regarding their

participation. Participants must sign the IRB-approved informed consent form prior to participation in any study specific procedure. The participant must receive a copy of the signed and dated consent document. The original signed copy of the consent document must be retained in the medical record or research file.

1. On the date of procedure consent at clinic or the date of surgery, patients will be given a paper consent form detailing about the outcome study with PTeye in addition to the consent for the surgical procedure that will be performed.
2. The key study personnel will briefly describe the PTeye and its application to the patient.
3. If the patient is interested in participating, the key study personnel will provide the patient with a paper-based consent form.
4. The key study personnel or the surgeon assigned to the patient will be available to discuss the protocol with the patient (including, risks, benefits, alternatives, etc.). The patient will also be provided with the contact information of the principle investigator should they have any questions.
5. If the patient consents to be part of the study, a scan of their signed consent form will be stored digitally in the patient's medical record.

Prior to surgery, the patient will be assigned a unique ID (e.g. Para_001). The unique ID will be utilized for randomly allocating the patient to the experimental arm (where the surgeon will use PTeye) or a control arm (where the surgeon will not use PTeye). The allocation will be conducted by the study coordinator using 'Random Allocation Software' (<http://mahmoodsaghaei.tripod.com/Softwares/randalloc.html>).

6.0 Study Procedures

For patients assigned to the study arm, the surgeon will use the PTeye as an intraoperative tool to identify if a suspect tissue is a parathyroid or not, during the parathyroid surgery. The surgeon will first take 5 baseline NIRAF measurements on the thyroid gland (or neck muscle, if thyroid is absent) using the disposable sterile fiber probe that is connected to the PTeye console (see Figure 1), as per device functionality requirements. The subsequent step would involve touching the target tissue in the neck with the fiber optic probe, following which the PTeye will indicate to the surgeon if the tissue is parathyroid or not. Parameters which are displayed on the PTeye console – Baseline values, Detection Intensity, Parathyroid Detection Ratio – will be recorded for each patient enrolled in the study arm. PTeye indicates that a tissue is parathyroid if it displays the 'Parathyroid Detection Ratio' is greater than 1.2. The rest of the surgical procedure will follow according to standard protocol.

For patients assigned to the control arm, the surgeon will not use the PTeye and will proceed with the parathyroid surgery as usual, while relying solely on her/his surgical experience in identifying the parathyroid glands during the operations.

Figure 1. A commercial fiber probe-based system (PTeye, [REDACTED]) for detecting near infrared autofluorescence (NIRAF) utilized for intraoperative parathyroid gland identification. PTeye consists of 1) the console that has a display and indicates to the surgeon if a tissue is parathyroid or not, 2) a detachable fiber optic probe, and 3) a foot-pedal which is activated by the surgeon for tissue NIRAF measurements.

De-identified information regarding (i) patient demographics, (ii) duration of surgery, (iii) number of frozen section (or PTH aspirate) analysis performed, (iv) frozen section (or PTH aspirate) and permanent histology reports of all excised tissues, (v) blood calcium levels (before surgery, 5-14 days after surgery and 6 months after surgery), (vi) parathyroid hormone (PTH) levels (5-14 days after surgery and 6 months after surgery) and (vii) postsurgical complications, if any and history of ER visits or hospitalization or repeat surgeries due to high or altered calcium levels, will be compiled for all enrolled patients. These parameters would then be compared between the study arm and the control arm to truly gauge the impact or value of a device like PTeye for parathyroid surgeries.

7.0 Risks

The clinical site is responsible for protecting all participants involved in human experimentation. This is accomplished through the IRB mechanism and the process of informed consent. The IRB reviews all proposed studies involving human experimentation and ensures that the participants' rights and welfare are protected and that the potential benefits and/or the importance of the knowledge to be gained outweigh the risks to the individual. The IRB also reviews the informed consent document associated with each study in order to ensure that the consent document accurately and clearly communicates the nature of the research to be done and its associated risks and benefits.

- The proposed study is designed to collect NIRAF measurements from neck tissues with a commercial device called PTeye during a parathyroidectomy. The device that will be used for NIRAF measurements is an FDA-cleared device.
- Each PTeye measurement takes less than 2 seconds, with the whole set of measurements not adding more than 5 minutes to the surgical procedure. Thus, there is a minimal increase of risk of surgery due to the potential five extra minutes

of anesthesia time associated with the study. In addition, the participating surgeon will evaluate the eligibility of the patient based on his or her medical condition. Patients with high anesthetic risks will not be asked to participate in the study.

- Since the power of near infrared light from PTeye will be extremely low, no side effects should be introduced to the patient.
- There should not be any discomforts, inconveniences, and/or risk resulting from this study.
- The study should not increase the risk of infection as a disposable sterile probe is used for each patient.
- The PTeye device used in this study has been FDA-cleared. The FDA clearance is granted based on the caveat that necessary precautionary measures will be taken by the surgeon to minimize the probable risks (as listed in the device brochure). The PTeye may be associated with unknown/unforeseen risks as with any other FDA-cleared medical devices used during surgical procedures.

8.0 Reporting of Adverse Events or Unanticipated Problems involving Risk to Participants or Others

Upon identification, adverse events resulting from this *in vivo* data acquisition procedure will be reported to the PI and IRB immediately. The study will be immediately terminated and not resumed until the sources leading to the adverse events are identified.

9.0 Study Withdrawal/Discontinuation

The data acquisition procedure will be terminated if the medical conditions of the participant show some unexpected and adverse changes. The decision of terminating the study will be determined by the participating surgeon.

10.0 Statistical Considerations

Currently there are no comparable published randomized trials that have evaluated the effect of NIRAF detection for reducing intraoperative frozen section analysis (or PTH aspirate) during parathyroidectomies. Based on preliminary data obtained from a similar ongoing study at Vanderbilt University Medical Center over 123 patients, an 83% reduction in frozen section analysis was observed in the interventional group of 63 patients where NIRAF was used, compared to the control group of 60 patients where NIRAF was not used (unpublished). The mean frozen section analysis (FSA) obtained for the NIRAF group is 0.1 FSA/patient versus 0.6 FSA/patient obtained in the control group. Assuming, that an expected mean difference of 0.6 FSA/patient needs to be observed between the NIRAF and the control group, where the standard deviation of the enrolled study population is 0.8 (Standard Deviation obtained in VUMC study population is 0.78 FSA/patient), 47 patients would be required per group (for a 95% powered study). Since this study may involve patient follow-up for data up to 6 months after surgery, we will thus assume an approximate data attrition rate of 15%, thus requiring a recruitment of 55 patients per group. Therefore, a total of 110 patients (study and control arm) should be recruited per surgeon for this study at this study site. Overall, 110

patients need to be enrolled at this study site under a single surgeon to assess the impact of this technology.

Sample size	
2-side significance level	0.05
Power (1-beta)	0.95
Ratio of sample size, Control/NIRAF group	1
Expected mean in NIRAF group	0.7
Expected mean in Control group	0.1
Study population standard deviation	0.8
Result	
Sample Size - Control group	47
Sample Size - NIRAF group	47
Sample Size – Control group compensated for 15% attrition	55
Sample Size – NIRAF group compensated for 15% attrition	55
Total sample size	110

Analysis Plan:

Continuous variables will be reported using medians and interquartile ranges (IQRs). Categorical variables will be reported using counts, percentages, and their 95% confidence intervals (CIs). Comparisons of the NIRAF and control parathyroidectomy groups for primary and secondary outcomes will be done using (a) 1-sided χ^2 or Fisher tests for categorical variables and (b) 2-tailed Student's t-test or Wilcoxon's test for continuous variables (depending on distribution of data). To analyze factors that influence the primary outcome assessed for this study, i.e., number of frozen sections specimens (or PTH aspirate) sent for analysis, a generalized linear mixed models will be used. The following variables will be considered as fixed effects for the study model: (i) nature of the intervention (NIRAF or control), (ii) age, (iii) BMI, (iv) number of intraoperative PTH assays, (v) number of diseased parathyroid glands seen, and (vi) type of parathyroid surgery (focused parathyroidectomy or bilateral neck exploration). The multivariate analysis based on this model will generate the respective odds ratios and their 95% CIs for the aforementioned factors that are being considered. A p-value ≤ 0.05 based on the statistical analysis for continuous/categorical variables under the primary and secondary outcomes measured in this study will be considered as significant.

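### The trial is sized on a difference of 0.6 frozen sections per patient, but the cited data give 0.5; the stated 95% power is then about 85% at 47 per arm

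*Combined protocol and SAP*

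**What the plan says.** All of this is in section 10.0, Statistical Considerations, of the combined protocol and SAP.

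- **Evidence.** The only source for the effect size is unpublished preliminary data from another centre: "The mean frozen section analysis (FSA) obtained for the NIRAF group is 0.1 FSA/patient versus 0.6 FSA/patient obtained in the control group". The same data are summarised as "an 83% reduction in frozen section analysis was observed in the interventional group of 63 patients where NIRAF was used".
- **Planning difference.** The calculation starts from: "Assuming, that an expected mean difference of 0.6 FSA/patient needs to be observed between the NIRAF and the control group". The SD is set at 0.8, against 0.78 in the preliminary data.
- **Result.** "47 patients would be required per group (for a 95% powered study". This is raised to 55 per group for 15% attrition, 110 in total.
- **Table.** The sample-size table lists "2-side significance level 0.05", then "Expected mean in NIRAF group 0.7" and "Expected mean in Control group 0.1".

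**The concern.** The preliminary figures agree with one another and imply a difference of 0.5. The planning value of 0.6 equals the preliminary control mean, not the difference between the arms. The table reaches 0.6 only by using a mean of 0.7, which appears nowhere else in the document, and it gives that mean to the device arm.

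The planning difference drives the 95% power, the 47, the 55 and the 110. A difference larger than the one observed is not a cautious choice, and the plan offers no clinical argument for it. If the trial ends without a significant result, a reader who trusts the stated 5% type II error would take that as stronger evidence against a benefit than the design can supply.

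**Working it through.** **Inputs (section 10.0).** Two-sided alpha 0.05; power 0.95; 1:1 allocation; SD 0.8 (preliminary 0.78); preliminary means 0.6 (control, 60 patients) and 0.1 (NIRAF, 63 patients); planning difference 0.6; attrition 15%. The analysis plan names a two-tailed t-test or Wilcoxon test for continuous variables.

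**1. Which difference do the cited data support?**
- 0.6 − 0.1 = 0.5, and 0.5/0.6 = 83.3%, which matches the quoted 83%.
- The table's means give (0.7 − 0.1)/0.7 = 85.7%, which does not.

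**2. Reproduce the plan's figure.** Normal approximation, n per arm = 2 × [SD × (1.960 + 1.645)/difference]².
- Difference 0.6: 2 × [0.8 × 3.605/0.6]² = 46.2, rounded up to 47. The noncentral-t calculation gives 47.2, with 94.9% power at 47.
- A one-sided calculation gives 39, so the plan did use a two-sided test.
- 47/0.85 = 55.3, which the plan takes as 55.

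**3. Change only the difference, to 0.5.** Power ≈ Φ(difference/[SD × √(2/n)] − 1.960).
- n = 47: 0.5/(0.8 × √(2/47)) = 3.030; Φ(1.070) = 85.8%. By t-test, 85.0%.
- n = 55: 0.5/(0.8 × √(2/55)) = 3.278; Φ(1.318) = 90.6%. By t-test, 90.1%.
- n for 95% power: 2 × [0.8 × 3.605/0.5]² = 66.5, or 67.5 by t-test, so 67 to 68 evaluable per arm.

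**4. Sensitivity (t-test power).** The within-arm SD of 0.74 applies if 0.78 is the SD over both preliminary arms together: √(0.78² − 0.25²) = 0.74.

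| Difference | SD | 47 per arm | 55 per arm |
|---|---|---|---|
| 0.5 | 0.8 | 85.0% | 90.1% |
| 0.5 | 0.78 | 86.8% | 91.5% |
| 0.5 | 0.74 | 90.0% | 94.0% |
| 0.54 | 0.8 | 89.9% | 93.9% |
| 0.45 | 0.8 | 77.0% | 83.2% |

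The 0.45 and 0.54 rows cover rounding. If the 83% was computed from unrounded means, means that round to 0.6 and 0.1 and give 83% differ by about 0.45 to 0.54. Rounding can therefore lower the power as well as raise it.

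**The case against.** Five points can be made for the plan.

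- **Attrition does not touch the primary outcome.** Section 2.0 counts frozen sections during the operation, so losses over six months need not reduce the number analysed. This stands. It makes 55 per arm, with about 90% power, the more realistic figure. But the plan attaches its 95% claim to 47, so 85% is the like-for-like comparison, and 90% is still short of 95%.
- **The SD may be smaller, or rounding may favour the plan.** Taken singly, neither reaches 95% (step 4). Taken together (difference 0.54, SD 0.74), t-test power is 93.8% at 47 and 96.7% at 55. So the most favourable combination, with every recruited patient analysed, would pass 95%; the plan does not argue for it.
- **The outcome is a sparse count, not a normal variable.** An arm with mean 0.1 cannot be normal with SD 0.8. As an illustration, take a negative binomial control arm (mean 0.6, SD 1.0) and a Poisson NIRAF arm (mean 0.1). The combined SD is then about 0.78. Simulated power is about 96% (t-test) and 93% (Wilcoxon) at 47 per arm, and 98% and 96% at 55. This also stands as a caution: true power depends on a distribution the document does not give. It cannot support the printed 95%, which was derived from a common SD of 0.8.
- **A design difference need not equal the pilot estimate.** True, but one larger than the pilot estimate needs a reason, and none is given.
- **The swapped labels are harmless to n.** Correct: the test is two-sided, with equal arms and a common SD, and the text makes the intended direction clear. The rows still contradict that text and should be corrected.

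**Conclusion.** The concern holds. The arithmetic from 0.6 and 0.8 to 47 is right; the input is not supported. Under the plan's own method and SD, the difference its data show gives 85.0% power at 47 per arm, a type II error of 15% instead of 5%, and 90.1% if all 55 per arm are analysed. These figures assume a two-sample t-test at two-sided 0.05, a common SD of 0.8 and a true difference of exactly 0.5. They are not a forecast of power for the real count distribution. The mismatch between the text (0.6 and 0.1) and the table (0.7 and 0.1, arms reversed) needs no assumption at all. The design remains usable at about 90%; the stated power and the table do not stand as written.

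**What to change.** In section 10.0:

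1. Set the table to control 0.6 and NIRAF 0.1, and change the planning difference in the text to 0.5.
2. Restate power as about 85% with 47 evaluable per arm and about 90% with all 55. Note that the primary outcome is recorded during surgery, so six-month attrition should not remove it.
3. Keep the total at 110.

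Alternatively, keep 0.6, give the reason for expecting a control mean of 0.7, and move 0.7 to the control row. If 95% power at a difference of 0.5 is truly required, the plan needs 67 to 68 evaluable patients per arm, which is more than it recruits.

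The first two routes need only an amendment to the wording and the table, with no extra patients. The cost of the first is a less favourable stated power.

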2.0 Rationale and Specific Aims

The goal of this study is to assess whether using PTeye – a NIRAF detection modality – can reduce healthcare associated costs after parathyroid surgeries and improve patient outcomes. The specific aims of this study is to determine if PTeye is beneficial or not for (i) intraoperative identification of parathyroid tissues, (ii) improving efficiency of parathyroid surgeries, and (iii) minimizing risk of postsurgical complications.

By being able to quickly and definitively locate parathyroid glands while in the operating room, the duration of surgical procedure could be further reduced. In addition, the number of frozen section biopsy (or PTH aspirate) and associated costs can be minimized. Furthermore, repeat surgeries as a result of missing a diseased parathyroid gland at the time of the initial parathyroidectomy for hyperparathyroidism could potentially be avoided.

Primary Outcome Measure:

1. Number of frozen sections (or PTH aspirate) sent for analysis
 - a. Number of frozen sections (or PTH aspirate) sent for analysis during the procedure to confirm potential parathyroid tissue [Time Frame: Immediate. During PTx procedure.]

Secondary Outcome Measure:

1. Persistent hyperparathyroidism (Immediate)

- a. Failure of intra-operative parathyroid hormone (PTH) to normalize (defined as failure of PTH to drop > 50% of its baseline value at final intra-operative PTH assay and/or failure of PTH to drop < 65 pg/ml or 6.9 pmol/L). [Time Frame: During parathyroidectomy (PTx) procedure]
- 2. Persistent hyperparathyroidism or hypercalcemia (transient)
 - a. Elevated blood calcium levels (total blood calcium level > 10.5 mg/dL or 2.6 mmol/L) with/without elevated parathyroid hormone (PTH) (serum intact PTH > 65 pg/ml or 6.9 pmol/L) at first postoperative visit. [Time Frame: 5-14 days after PTx procedure]
- 3. Persistent hyperparathyroidism or hypercalcemia (failed parathyroidectomy)
 - a. If blood calcium with/without parathyroid hormone (PTH) has not normalized at 1st post-operative visit, calcium and/or PTH is subsequently measured as necessary. Patient is defined to have a failed parathyroidectomy if hypercalcemia/hyperparathyroidism (defined as total blood calcium level > 10.5 mg/dL or 2.6 mmol/L, with/without elevated serum intact PTH > 65 pg/ml or 6.9 pmol/L) persists at or after the 6th postoperative month. [Time Frame: 6 months after PTx procedure]
- 4. Overall number of parathyroid glands identified

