- a. Number of doctor visits/emergency department visits or hospital admissions due to persistent hypercalcemia and/or associated symptoms after parathyroidectomy procedure [Time Frame: Up to 6 months after PTx procedure.]
15. Number of patients who have had repeat parathyroidectomy (PTx) procedure
 - a. Number of patients with repeat PTx procedure performed after the current procedure [Time Frame: 6 - 12 months after PTx procedure.]

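### Yes/no secondary outcomes are tested one-sided at p ≤ 0.05, with no direction or reason given, while continuous outcomes and the sample size use a two-sided 0.05

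*Combined protocol and SAP*

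**What the plan says.** One sentence of the Analysis Plan (Section 10.0) sets two standards for comparing the arms: "1-sided χ^2 or Fisher tests for categorical variables" and "2-tailed Student's t-test or Wilcoxon's test for continuous variables". The section then states a single rule, that p ≤ 0.05 for continuous or categorical variables "under the primary and secondary outcomes measured in this study will be considered as significant". The sample size table in the same section lists a "2-side significance level" of 0.05.

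The primary outcome, frozen sections or PTH aspirates per patient, is a count and was sized as a difference in means. In practice the categorical tests therefore apply to the yes/no secondary outcomes in Section 2.0:

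- persistent hyperparathyroidism during surgery (item 1);
- persistent disease at the first postoperative visit (item 2);
- failed parathyroidectomy at 6 months (item 3);
- "Number of patients who have had repeat parathyroidectomy (PTx) procedure" (item 15).

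The documents state neither a direction nor a justification for the one-sided tests. Section 2.0 names "minimizing risk of postsurgical complications" among the aims, which hints at a direction favouring NIRAF. The same sentence, however, asks whether the device helps or does not, which leaves the question open.

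**The concern.** A one-sided test at 0.05 uses the same critical value as a two-sided test at 0.10. The outcomes closest to patient benefit, failed and repeat operations, are thus held to a looser nominal standard than operating time or nights in hospital.

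Three consequences follow:

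- A favourable difference in failures can be called significant on a result that a two-sided test would not support.
- If the direction is taken to favour NIRAF, an excess of failures in the NIRAF arm cannot be declared, although harm is a possible answer to the question in Section 2.0.
- If the direction is settled only after the data are seen, the nominal total error is 10%.

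The planned 95% CIs do not close the gap. For categorical variables they are attached to counts and percentages, not to the difference between arms, and the model's odds ratios concern frozen sections only.

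**Working it through.** **Inputs.** From Section 10.0: mean difference 0.6, SD 0.8, power 0.95, two-sided 0.05, 47 per arm, and 55 per arm after 15% attrition. From Section 1.0: failed operations in 5–10% of cases. The true rates in the power example (step 5) are assumptions.

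**1. The plan's own sample size is two-sided.** n = 2[σ(z₁₋α/₂ + z₁₋β)/δ]² = 2[0.8 × (1.960 + 1.645)/0.6]² = 46.2, rounded up to 47, as stated. A one-sided 0.05 replaces 1.960 with 1.645 and gives 38.5, rounded up to 39. The table label and the arithmetic agree.

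**2. Splits on which the verdict turns** (55 per arm, NIRAF v control failures). A control rate of 5–10% means 3 to 5 failures in 55.

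- Fisher, 0 v 5: one-sided p = C(55,5)/C(110,5) = 0.0284. With equal arms the two-sided p is twice this, 0.0568.
- Uncorrected χ², read one-sided as a signed z, where z = (difference in proportions)/√[p̄(1−p̄)·2/55]. For 0 v 3, p̄ = 3/110 and z = 1.756, giving p = 0.040 one-sided and 0.079 two-sided. For 1 v 5, p̄ = 6/110 and z = 1.679, giving 0.047 and 0.093.

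**3. Actual error in the favourable direction.** This is the summed binomial probability of all significant tables favouring NIRAF when both arms share the same event rate.

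| Test | Per arm | Event rate | One-sided 0.05 | Favourable tail of two-sided 0.05 |
|---|---|---|---|---|
| Fisher | 55 | 5% | 1.3% | 0.4% |
| Fisher | 55 | 10% | 2.6% | 1.0% |
| χ² | 55 | 5% | 6.0% | 2.2% |
| χ² | 55 | 10% | 5.1% | 2.5% |
| Fisher | 47 | 5% | 1.0% | 0.3% |
| Fisher | 47 | 10% | 2.3% | 0.8% |
| χ² | 47 | 5% | 5.9% | 2.6% |
| χ² | 47 | 10% | 5.3% | 3.0% |

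If the direction is chosen after seeing the data, the one-sided rates double. At 55 per arm the total error is 2.6% and 5.3% with Fisher, and 12.1% and 10.3% with χ², at event rates of 5% and 10%.

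**4. Harm.** With 9 failures on NIRAF and 1 on control (55 per arm), Fisher's test for benefit gives p = 0.999; two-sided it gives 0.016.

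**5. Power given up by testing two-sided.** Assuming true failure rates of 1% (NIRAF) and 10% (control), Fisher power falls from 49% to 34% at 55 per arm, and from 38% to 23% at 47 per arm.

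**The case against.** The strongest reply is that little changes in practice.

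- **Fisher is conservative.** Its actual one-sided error of 1.3–2.6% at 55 per arm is about the 2.5% that a two-tailed 0.05 test allows in one direction. This stands: with Fisher, the laxity is mainly nominal. But the plan also permits χ², gives no rule for choosing between the two, and one-sided χ² exceeds 5% at both event rates.
- **The χ² splits are sparse.** Expected failures per arm are 1.5 for 0 v 3 and 3 for 1 v 5. Many analysts would use Fisher there, which gives one-sided p = 0.12 and 0.10, so the verdict would not change. This stands too, and 0 v 5 is the robust example.
- **Failure and repeat surgery are late outcomes**, so about 47 per arm may be evaluable. The 0 v 5 verdict still turns at 47 (0.028 and 0.056), though 5/47 = 10.6% is just above the 5–10% range. The χ² error ratio at a 10% event rate drops to 1.8 (5.3/3.0), so a doubling cannot be claimed there.
- **The harm example is extreme.** Its rates are 9/55 = 16.4% and 1/55 = 1.8%, both outside 5–10%. It illustrates the blind spot and is not a forecast. Reported counts would show such an excess, but no planned test would flag it.
- **A χ² test has no direction of its own**, so the one-sided label may be loose wording. If so, the text still needs correcting, because it does not define the test.

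**Conclusion.** The concern holds. The Analysis Plan applies one p-value threshold to tests of different sidedness, against a two-sided design level, without giving a direction or a reason. Nominally, the error allowed in the favourable direction is 5% for yes/no outcomes and 2.5% elsewhere. The actual error depends on the test: Fisher stays near or below 2.6%, while uncorrected χ² runs at 5–6%. At least one plausible result, 0 v 5 failures in 55 per arm, changes from significant to non-significant under a two-sided test. An excess of failures on NIRAF could not be declared if the direction favours NIRAF.

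The figures assume that failure rates lie in the 5–10% range of Section 1.0 and that a one-sided χ² means a signed z test. The finding is confined to secondary outcomes; the primary comparison and the 47 or 55 per arm are unaffected. It should be corrected before analysis.

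**What to change.** In the Analysis Plan, make the χ² and Fisher tests two-sided at 0.05. For each yes/no outcome, report the between-arm risk difference with a two-sided 95% CI, so that a difference in either direction is visible.

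This is a wording change and does not alter the sample size. The cost is the loss of power shown in step 5, on outcomes for which the trial was not sized.

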 - a. Overall number of parathyroid glands identified (Experimental Group: Glands identified with naked eye + NIRAF; Control Group: Glands identified with naked eye) [Time Frame: Immediate. During PTx procedure.]
- 5. Number of parathyroid glands identified with NIRAF
 - a. Number of parathyroid glands identified with NIRAF, which was not seen with surgeon's naked eye [Time Frame: Immediate. During PTx procedure.]
- 6. Number of diseased parathyroid glands identified versus preoperatively localized glands
 - a. Number of diseased parathyroid glands identified intra-operatively versus glands localized preoperatively using sestamibi, CT or ultrasound [Time Frame: Preoperative to immediate during PTx procedure.]
- 7. Number of intra-operative parathyroid hormone (PTH) assays sent
 - a. Number of intra-operative parathyroid hormone assays sent during the procedure [Time Frame: Immediate. During PTx procedure.]
- 8. Duration taken to identify first parathyroid gland
 - a. Duration taken to identify 1st parathyroid gland in PTx procedure – timed from skin incision to finding PG. [Time Frame: Immediate. During PTx procedure.]
- 9. Duration taken to identify last parathyroid gland
 - a. Duration taken to identify last parathyroid gland in PTx procedure – timed from skin incision to finding the last PG. [Time Frame: Immediate. During PTx procedure.]
- 10. Duration of parathyroidectomy (PTx) procedure
 - a. Duration of PTx procedure – timed from skin incision until the surgeon notifies the anesthesia team to awaken the patient [Time Frame: Immediate. During PTx procedure.]
- 11. Duration taken for intraoperative parathyroid hormone (PTH) to normalize
 - a. Time taken for PTH to attain cure criteria or normalize - timed from skin incision until the PTH levels drops > 50% of its baseline value and/or PTH drops < 65 pg/ml or 6.9 pmol/L. [Time Frame: Immediate. During PTx procedure.]
- 12. Number of nights spent in the hospital after parathyroidectomy
 - a. Number of nights spent for postoperative recovery in the hospital after the surgical procedure. [Time Frame: 0-72 hours after PTx procedure.]
- 13. Number of 'false positive' tissues excised by surgeon
 - a. Number of tissues that were excised by surgeon assumed to be parathyroid tissue, but is later validated as nonparathyroid tissue (false positive) by histology [Time Frame: Immediate to 10 days after PTx procedure.]
- 14. Number of doctor visits/emergency department visits or hospital admissions

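### Preoperative localisation, which secondary outcome 6 already requires, should be a prespecified baseline covariate in the between-arm comparisons; the gain is modest but nearly free

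*Combined protocol and SAP*

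**What the plan says.** Localisation has one role in the plan, as the comparator in secondary outcome 6 (section 2.0): "Number of diseased parathyroid glands identified intra-operatively versus glands localized preoperatively using sestamibi, CT or ultrasound". The text does not say whether this is a difference, a ratio or a measure of agreement.

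Section 5.0 names a software tool for allocation and no stratum or block: "The unique ID will be utilized for randomly allocating the patient to the experimental arm". The ID is assigned before surgery. The section does not say that imaging is complete by then.

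Section 10.0 compares continuous outcomes between arms with a t-test or Wilcoxon test, without covariates. A generalised linear mixed model then examines what influences the number of frozen sections: "The following variables will be considered as fixed effects for the study model: (i) nature of the intervention (NIRAF or control), (ii) age". The other fixed effects are BMI, number of intraoperative PTH assays, number of diseased glands seen, and focused versus bilateral surgery. Localisation is not among them.

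The list in section 6.0 of data to be compiled does not name imaging results.

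**The concern.** Section 1.0 says surgeons send tissue for frozen section when they doubt its identity. A patient whose imaging has shown no gland plausibly means a longer search and more doubt, hence more specimens. That makes localisation a candidate prognostic factor for the primary outcome and for the gland-count and timing outcomes (4 and 8-11). PTeye is used only during the operation, so it cannot alter a preoperative scan, and adjusting for the scan result is safe.

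The plan's covariate choice runs the other way. The factor model omits this preoperative variable but adjusts for two that arise during surgery. One of them, the number of PTH assays, is itself secondary outcome 7. Both could be affected by the device, so conditioning on them can distort the arm effect.

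At stake are some precision in a 110-patient trial and the definition of outcome 6, which cannot be analysed as written because no metric is given.

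**Working it through.** **Plan's figure.** Inputs from section 10.0: 0.05 as the "2-side significance level"; "47 patients would be required per group (for a 95% powered study"; "an expected mean difference of 0.6 FSA/patient needs to be observed between the NIRAF and the control group"; "the standard deviation of the enrolled study population is 0.8". Then n = 2 × [0.8 × (1.960 + 1.645) / 0.6]² = 46.2, so 47 per group. The figure reproduces, and the missing covariate does not make it wrong. With SE = 0.8 × √(2/47) = 0.165, power is 95.3% at a difference of 0.6. The preliminary data show 0.5 ("The mean frozen section analysis (FSA) obtained for the NIRAF group is 0.1 FSA/patient versus 0.6 FSA/patient obtained in the control group"), for which power is 85.8%.

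**Assumed inputs (not in the documents).** The share not localised, p, is 0.2 or 0.3. The ratio R of frozen-section means, not localised to localised, is 2, 3 or 4 in both arms. The control mean is held at 0.6 and the device mean at 0.1, so the gap between strata in the device arm is 1/6 of the control gap. The SD of 0.78 is the one section 10.0 gives for the preliminary study population.

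**Formulas.**
- Localised control mean: m = 0.6 / [(1 − p) + pR].
- Control gap: g = m(R − 1).
- Gap averaged over arms: a = g × (1 + 1/6) / 2.
- Variance share recovered by adjustment: s = p(1 − p)a² / 0.78².
- Adjusted SD for power: 0.8 × √(1 − s). The SE falls by 1 − √(1 − s).

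Example, p = 0.2 and R = 2: m = 0.6/1.2 = 0.5; g = 0.5; a = 0.292; s = 0.16 × 0.0851 / 0.608 = 0.022; the SE falls by 1.1%.

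| p | R | g | a | s | SE falls by | Power at 0.5 | Power at 0.6 |
|---|---|---|---|---|---|---|---|
| 0.2 | 2 | 0.50 | 0.292 | 2.2% | 1.1% | 86.5% | 95.7% |
| 0.2 | 3 | 0.86 | 0.500 | 6.6% | 3.3% | 88.0% | 96.4% |
| 0.2 | 4 | 1.13 | 0.656 | 11.3% | 5.8% | 89.6% | 97.1% |
| 0.3 | 2 | 0.46 | 0.269 | 2.5% | 1.3% | 86.6% | 95.8% |
| 0.3 | 3 | 0.75 | 0.438 | 6.6% | 3.4% | 88.0% | 96.4% |
| 0.3 | 4 | 0.95 | 0.553 | 10.5% | 5.4% | 89.3% | 97.0% |

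Powers are for 47 per arm, by the normal approximation on the mean-difference scale. A count regression would not match them exactly.

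**Chance imbalance.** With 55 per arm, the 95% range for the imbalance in share not localised is ±1.96 × √[2p(1 − p)/55], or ±0.150 to ±0.171. Multiplied by a, this moves the estimated difference by ±0.044 to ±0.098. The unadjusted 95% half-width is 1.96 × 0.78 × √(2/55) = 0.292. The squared ratios, (0.044/0.292)² to (0.098/0.292)², are again about 2-11%. The shift is therefore part of the unadjusted standard error and not an addition to it.

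**Outcome 6.** Let ρ be the correlation between the counts identified and localised, and k the ratio of their SDs (localised to identified); neither is in the documents. Relative to the raw identified count, a difference score has variance 1 + k² − 2ρk, and the count adjusted for the number localised has 1 − ρ². The first exceeds the second by (k − ρ)², which is never negative. With k = 1 the values are 2.00 against 1.00 at ρ = 0, 1.00 against 0.75 at ρ = 0.5, and 0.20 against 0.19 at ρ = 0.9.

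**The case against.** The strongest case against is that this is one optional covariate with an assumed effect. The documents give no non-localisation rate and no link between localisation and frozen sections; section 1.0 says only that imaging performs variably and may not match the operative view. Focused versus bilateral surgery may already be a partial proxy, if it means the planned approach. All of this stands. It limits the size of the point but not its direction, and any proxy enters only the factor model, not the arm comparisons.

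Four stronger readings are tempting, and the documents do not support them.

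- A reader might infer that localisation accounts for 7-33% of the variance. Under the same assumptions that is p(1 − p)g² / 0.78², which is 0.040/0.608 to 0.202/0.608. It uses the control-arm gap alone, and 0.78 is not a control-arm SD. For the arm difference the share is 2-11%.
- A reader might take the chance shift of 0.044-0.098 as bias. It is random and already inside the standard error.
- A reader might infer that imaging error makes outcome 6 unreadable as a device effect. Imaging error unrelated to arm adds variance, not bias: the expected arm difference in identified minus localised equals that in identified. With equal SDs, the difference score is noisier than the raw count only when ρ is below 0.5.
- A reader might take localisation as known to be fixed before allocation. That is likely but not stated.

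**Conclusion.** The point holds as a low-cost improvement. The plan leaves a plausible preoperative prognostic factor out of the between-arm comparisons and out of the factor model, while that model adjusts for variables arising during surgery. Outcome 6 has no metric.

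With 20-30% not localised and a 2-4-fold mean ratio, adjustment lowers the SE by about 1-6%. The power gain is about 1-4 points at a difference of 0.5 and up to about 2 points at 0.6. A weaker link would give less and a stronger one more; at an explained share of 20%, power at 0.5 would be 92.3%. The omission does not bias the primary comparison, and the sample size does not need to change on this account.

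**What to change.** 1. Record before allocation whether imaging localised a gland (yes/no) and how many, and add this to the data list in section 6.0.
2. Make the between-arm analysis of the primary outcome a prespecified adjusted one, for example a count regression with arm and localisation. State that it replaces the unadjusted t-test or Wilcoxon test. Adding localisation only to the factor model would leave the primary comparison unchanged. Keep PTH assays and diseased glands seen out of this model.
3. Adjust outcomes 4 and 8-11 for localisation in the same way.
4. Define outcome 6 as the number of diseased glands identified, compared between arms with the number localised as covariate. This keeps the plan's endpoint and supplies the missing metric.
5. Stratifying allocation on localisation is optional. It balances the arms only if the list within each stratum is blocked.

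The cost is one data field and one covariate, using information that outcome 6 already requires.
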